4.1 OVERVIEW OF STUDY DESIGN/INTERVENTION

4.2 Design

This is a non-therapeutic pilot study performing ¹¹C-CH PET imaging of patients with high-grade gliomas who develop MRI findings consistent with recurrent tumor and/or pseudo-progression within 24 weeks after completion of treatment with radiation (with or without concurrent therapy). The objective of this trial is to correlate ¹¹C-CH PET SUV measures with MRI follow-up outcomes. Each patient will be followed up for at least 11 months after completion of the PET scan to confirm MRI changes as representing pseudoprogression or true tumor progression. This study will not be used to make a clinical diagnosis or to change treatment decisions. Six patients will be enrolled on this study over a 1 year period.

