4.3 Intervention

This study will enroll patients with a histologically confirmed diagnosis of a high-grade glioma. Eligible patients must have undergone standard radiation (typically 60Gy in 30 fractions), with or without concurrent drug therapy, and have MRI findings consistent with tumor progression and/or pseudoprogression within 24 weeks after completion of radiation. Eligible patients will undergo an ¹¹C-CH PET study within 2 weeks of the standard of care MRI that shows changes concerning for tumor progression vs. pseudoprogression. All patients will then be followed with surveillance brain MRI with and without contrast as per standard of care for a period of 11 months, to assess further progression or stabilization of the lesion. Initial MRI changes are considered to represent pseudoprogression/treatment related changes if the lesion stabilizes or becomes smaller without a change in tumor-related therapy. Otherwise, it will be considered a recurrence should there be progressive radiographic changes.

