Radiographic changes will be defined as progression rather than pseudoprogression within that 24 week window per modified RANO criteria. However, unlike the RANO criteria, the protocol will allow for a broader window of 24 weeks after completion of radiation instead of 12 weeks to maximize enrollment. Progression can only be defined using diagnostic imaging less than 24 weeks after completion of radiation if there is new enhancement outside the radiation field (beyond the high-dose region or 80% isodose line) or if there is unequivocal evidence of viable tumor or histopathologic sampling (ie, >70% tumor cell nuclei in areas, high or progressive increase in MIB-proliferation index compared with prior tissue, or evidence for histologic progression or increased anaplasia in tumor). Given the difficulty of differentiating true progression from pseudoprogression, clinical decline alone, in the absence of radiographic or histologic confirmation of progression, will not be sufficient for definition of progressive disease in the first 24 weeks after completion of radiation. Follow-up brain MRI with and without contrast per standard of care will be used in the assessment of the evolution of these lesions. Further increase in enhancement in subsequent MRI warranting a change in therapy per the treating physician will define progression unless proven otherwise by a histopatholgically confirmed diagnosis. Lesions that stabilize or reduce in size will be deemed consistent with pseudoprogression.

Radiation Exposure (dosimetry). Radiation exposure from ¹¹C-CH PET imaging study has been estimated and published.[55, 56] The critical organ exposures are: kidney 0.64, bladder wall 0.36, and liver 0.26 cGy/mCi with all other organs receiving less than 0.25 cGy per mCi injected. Doses to the most radiation sensitive tissues red marrow, testes and ovaries are 0.075, 0.057, and 0.067 cGy/mCi respectively. The RDRC requires that the administered activity result in <30mSv to the

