11.0 BIOSTATISTICS

This trial is a pilot study to determine the distribution of ^{11}C -CH using PET imaging in progressive high-grade glioma lesions suspected to represent true tumor progression vs pseudo-progression, following treatment with a course of radiation. The purpose of this trial is to correlate SUV measures from ^{11}C -CH PET with evolving changes on brain MRI in high-grade glioma after radiotherapy. In a small subgroup of patients required surgery, tissue will be analyzed for histopathologic correlate. The data gathered will not be considered definitive, but rather will be used to as preliminary data in support of a larger, definitive study.

The biodistribution of ^{11}C -CH will be measured using PET as a basis for dosimetry. This will be performed with region of interest analysis. The first objective is to determine the organ/tissue uptake and tumor localization following intravenous injection of ^{11}C -CH in patients with high-grade glioma with radiographic progression concerning for progression versus pseudoprogression following treatment with radiation with or without chemotherapy. The group for this analysis comprises 6 high-grade glioma patients who appear to have progression vs pseudoprogression on standard MRI with contrast. Standardized uptake values (SUV) in the brain will be measured and summarized for each patient to describe the organ and tissue uptake of the tracer. The mean SUV along with SUVmax value will be estimated in normal and tumor tissue, and lesion-to-normal brain ratio (LNR) values will be obtained. All patients will then be followed with surveillance brain MRI per standard treatment over a period of 11 months for evolving changes that will confirm the diagnosis of progression versus pseudoprogression as defined in the protocol.

It is anticipated that 1 patient every 2 months will be accrued to this study and the study will be completed in approximately 12 months.

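### Sections 4.3 and 7.2 define progression and pseudoprogression differently, so two kinds of follow-up course get a label in one section and none in the other

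*Combined protocol and SAP*

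**What the plan says.** Section 4.3 (Intervention) treats the initial MRI changes as pseudoprogression "if the lesion stabilizes or becomes smaller without a change in tumor-related therapy". It continues: "Otherwise, it will be considered a recurrence should there be progressive radiographic changes". Pseudoprogression therefore carries a therapy condition and recurrence does not.

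Section 7.2 (¹¹C-CH PET imaging and injection) places the condition on the other class. A further rise in enhancement "in subsequent MRI warranting a change in therapy per the treating physician will define progression unless proven otherwise" by histopathology. For the other class it says only: "Lesions that stabilize or reduce in size will be deemed consistent with pseudoprogression".

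Section 11.0 (Biostatistics) relies on "evolving changes that will confirm the diagnosis of progression versus pseudoprogression as defined in the protocol" and names neither section. Section 9.0 compares peak SUV and tumor-to-background ratio with the follow-up outcome on MRI. On size and duration, Section 4.2 states "Six patients will be enrolled on this study over a 1 year period" and "Each patient will be followed up for at least 11 months after completion of the PET scan".

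**The concern.** The label is the reference standard for the second primary objective, so it decides which patients enter each side of the SUV comparison. If two sections label the same patient differently and the statistics section does not choose, the class counts are not determined by the plan. The choice could also be made after the SUVs are known.

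Section 7.2 makes progression depend partly on a management judgement, which can differ between patients whose lesions behave alike. Section 4.3 does something similar for pseudoprogression. With six patients, one ambiguous label is a visible part of the data.

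**Working it through.** **Inputs.** The two rules as written in 4.3 and 7.2; six patients (Section 4.2); follow-up of at least 11 months after PET (Section 4.2). The only stated planning figure that can be checked is accrual: Section 11 says "It is anticipated that 1 patient every 2 months will be accrued to this study", and 6 × 2 = 12 months, which agrees with the stated one year. The sample size has no power or precision basis to reproduce.

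**Step 1: apply both rules.** Assume no histology is available, and take growth to mean a further rise in enhancement, so that the imaging part of both rules is met.

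| Course on follow-up MRI | Therapy | Section 4.3 | Section 7.2 |
|---|---|---|---|
| Growing | change judged warranted | recurrence | progression |
| Growing | change not judged warranted | recurrence | no label |
| Stable or smaller | no change made | pseudoprogression | pseudoprogression |
| Stable or smaller | change made | no label | pseudoprogression |

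The sections agree in rows 1 and 3 and disagree in rows 2 and 4. In row 4, the fallback in 4.3 does not help, because it requires progressive changes on imaging.

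**Step 2: look for a rule that resolves it.** Section 11 does not choose. The PET imaging text in 7.2 plans six evaluable subjects but does not define evaluable. The one replacement rule, in Section 6.0, concerns inadequate surgical tissue. No section provides an indeterminate class.

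**Step 3: check whether follow-up is long enough to matter.** Before week 24, Section 7.2 restricts an imaging-based diagnosis of progression to new enhancement outside the radiation field. Eleven months is 11 × 365.25 / 12 / 7 = 47.8 weeks. Even a PET scan at week 0 after radiation leaves 47.8 − 24 = 23.8 weeks of follow-up beyond that window. Every patient followed as planned therefore has follow-up time outside the early restriction.

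**Step 4: the weight of one patient.** One unlabelled patient is 1/6 = 16.7% of the sample; two are 2/6 = 33.3%. As an illustration, take four growing lesions, one of them in row 2, and two stable or smaller lesions, one of them in row 4:

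- Section 4.3: 4 recurrence, 1 pseudoprogression, 1 unlabelled.
- Section 7.2: 3 progression, 2 pseudoprogression, 1 unlabelled.

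Each section labels five patients, but not the same five. No test is planned. Purely as a gauge of information, the smallest attainable two-sided exact rank p-value is 2/C(6,2) = 0.133 for a full 4:2 split, 2/C(5,2) = 0.20 for 3:2, and 2/C(5,1) = 0.40 for 4:1.

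**The case against.** **The sections can be read together.** Section 4.3 is a design overview with no threshold for progressive change, and 7.2 could be supplying one: growth large enough to warrant a change. The follow-up sentence in 7.2 also says what will define progression, not that nothing else can. This is a fair reading, but it does not close the gap. Growth below that threshold is still not pseudoprogression under 7.2, which asks for a stable or smaller lesion. It also leaves row 4 untouched.

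**The gap in 7.2 is narrower than it may seem.** A reader might infer that any growing lesion whose therapy was not changed is unlabelled. The text asks whether growth warrants a change in the physician's view, not whether a change was made. Growth that warrants a change that is then not made is still progression.

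**Such cases may be rare.** Section 3.0 recommends continued therapy with monitoring when pseudoprogression is suspected, but because enhancement then typically stays stable or improves. It also says recurrence needs more aggressive management. This makes row 2 possible without showing that it is common. Tissue would also settle some cases. Section 6.0 expects all six patients to need resection, while Section 11 expects surgery in a small subgroup, so how much tissue there will be is unclear.

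**Materiality is modest.** This is a descriptive pilot that the protocol says will not be definitive. Management may not depend on the PET result, so the documents give no ground for inferring that SUVs would steer the physician's judgement. The biodistribution objective is unaffected. All of this stands, and it limits the severity rather than removing the conflict.

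**Conclusion.** The point holds as a conflict between two definitions of the same outcome label, in both directions, with nothing in the plan to resolve it. It rests on the wording of 4.3, 7.2 and 11 and on the absence of histology for the patient concerned. It should be corrected, but it does not undermine the study.

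Its size is one sixth of the sample per affected patient; the documents give no rate. A reader might want a probability. If 60–70% of patients are true progressors (the complement of Section 6.0's 30–40% pseudoprogression) and an assumed 10% to 30% of those fall in row 2, the chance of at least one among six is 1 − (1 − 0.60 × 0.10)⁶ = 31% at the low end and 1 − (1 − 0.70 × 0.30)⁶ = 76% at the high end. That range depends on the assumed share, ignores row 4 and supposes no tissue for anyone, so it should not be quoted as an estimate.

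A reader might also infer that unlabelled patients drop out of the SUV comparison. The documents do not say so: Section 11 summarizes SUV for every patient. What is missing is any statement of how a patient without a label enters the comparison.

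**What to change.** Reconcile 4.3 and 7.2 into one outcome-label definition, fix it before SUVs are compared with outcomes, and cite it by section number in Section 11.

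- Base the label on the evolution of the scanned lesion on follow-up MRI, and keep the histology override now in 7.2.
- Record therapy change as separate data, with one variable for judged warranted and one for made, rather than as a condition for either class.
- Report any patient who fits neither class as indeterminate, with that patient's SUV and lesion ratio. Include here a lesion that is stable or smaller after a therapy change, since its course may reflect the new treatment.
- Repeat the SUV comparison with each indeterminate patient placed in each class in turn.

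The cost is wording in three sections and two database variables, with no extra scans, staff or patients. The drawback is that some growth the physician would have disregarded may count as progression, unless the definition also sets a size rule. The change concerns only the outcome label and implies no view on when therapy should change.

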Differentiating between true progression and pseudo-progression provides critical information to guide patient management decisions. In patients with pseudo-progression, the imaging findings represent treatment-related inflammatory changes secondary to a robust response to therapy and continued treatment is appropriate and beneficial. For patients in whom pseudo-progression is suspected, continued therapy with close monitoring is recommended as the contrast enhancement will typically remain stable or improve.[4] For patients who are symptomatic from a growing lesion in an eloquent portion of the brain, observation is not feasible, and the prompt diagnosis of tumor progression versus pseudo-progression is imperative to ameliorate and prevent further disability. Tumor recurrence needs to be managed more aggressively to prevent growth, and early identification of recurrence could impact a patient’s overall prognosis and survival. An accurate assessment of treatment response is also fundamental in clinical trials and is becoming increasingly relevant with the growing interest in immunotherapies for high-grade gliomas.

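### Sections 4.3 and 7.2 define pseudoprogression differently, so a lesion that is stable or smaller after a therapy change is pseudoprogression under one and has no label under the other

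*Combined protocol and SAP*

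**What the plan says.** Two sections define the follow-up outcome.

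- **Section 4.3 (Intervention).** The initial MRI change is pseudoprogression "if the lesion stabilizes or becomes smaller without a change in tumor-related therapy". Otherwise it is a recurrence, but only where radiographic changes are progressive.
- **Section 7.2 (PET imaging and injection).** On follow-up MRI, "Further increase in enhancement in subsequent MRI warranting a change in therapy per the treating physician will define progression", unless histopathology shows otherwise. The next sentence reads: "Lesions that stabilize or reduce in size will be deemed consistent with pseudoprogression". It carries no condition on therapy.

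Section 7.2 also restricts early calls of progression. It says "Progression can only be defined using diagnostic imaging less than 24 weeks after completion of radiation if there is new enhancement outside the radiation field" and then adds the alternative "or if there is unequivocal evidence of viable tumor or histopathologic sampling". In the same 24 weeks, "clinical decline alone, in the absence of radiographic or histologic confirmation of progression, will not be sufficient for definition of progressive disease".

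The label is used in the second primary objective (Section 2.1), which relates SUV measures to MRI follow-up outcome, and in Section 9.0, which compares peak SUV and tumor-to-background ratio with that outcome. Section 11.0 says the diagnosis follows the protocol's definition and names neither section.

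**The concern.** The MRI label is the reference standard for the SUV comparison. A lesion that is stable because treatment was changed is not evidence that the original MRI change was inflammatory. Section 4.3 recognises this and Section 7.2 does not.

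Under the protocol's hypothesis a recurrence has high uptake. Counting one as pseudoprogression puts a high value in the low-uptake group and pulls the comparison toward no difference. With about two pseudoprogression cases expected, one wrong label weighs heavily. The data are also meant to support a larger study, so an unsettled definition could be carried forward. The distribution objective does not depend on the label and is unaffected.

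**Working it through.** **Step 1. Apply both definitions to each course.**

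| Course after the index MRI | Section 4.3 | Section 7.2 |
|---|---|---|
| Stable or smaller, therapy unchanged | Pseudoprogression | Pseudoprogression |
| Further enhancement that prompts a therapy change | Recurrence | Progression, unless histology shows otherwise |
| Tissue meeting the histologic criteria before week 24 | Not addressed | Progression |
| Therapy changed or lesion resected without further enhancement and without qualifying histology; then stable or smaller | No label: the therapy condition fails, and there are no progressive changes | Pseudoprogression |

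The sections conflict only in the last row.

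**Step 2. Inputs for the size.** N = 6 (Section 11.0). The share with pseudoprogression is 30-40% (Section 6.0), so 6 × 0.30 = 1.8 to 6 × 0.40 = 2.4 cases are expected. True splits of 2 vs 4 and 3 vs 3 (pseudoprogression vs recurrence) are used as illustrations. The plan states no figure of its own to reproduce.

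**Step 3. Effect of one mislabelled recurrence.** Let D be the true difference in mean SUV (recurrence minus pseudoprogression) and n the number of true pseudoprogression cases. Assume the mislabelled patient is random with respect to uptake among recurrences.

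- The expected mean of the labelled pseudoprogression group rises by D/(n+1).
- The expected mean of the remaining recurrences is unchanged.
- The expected difference is therefore D − D/(n+1), a proportional loss of 1/(n+1).
- n = 2: 1/3 = 33%. n = 3: 1/4 = 25%.

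As a check on scale only, take the mean SUVmax values in Table 1 (1.89 and 0.59, for a different tracer and population). With n = 2 the labelled pseudoprogression mean becomes (2 × 0.59 + 1.89)/3 = 1.02. The difference falls from 1.30 to 0.87, a loss of one third.

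**Step 4. Precision cost of setting that patient aside.** The baseline is the grouping that Section 7.2 would produce. With equal variances the standard error of the difference is proportional to √(1/a + 1/b), where a and b are the group sizes.

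- True 2 vs 4 is labelled 3 vs 3: √(1/3 + 1/3) = 0.816. Set aside, 2 vs 3: √(1/2 + 1/3) = 0.913. Ratio 1.118, about +12%.
- True 3 vs 3 is labelled 4 vs 2: √(1/4 + 1/2) = 0.866. Set aside, 3 vs 2: 0.913. Ratio 1.054, about +5%.

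**The case against.** The best defence is that the two sections can be read together. Section 7.2 is silent on lesions that stabilise after a therapy change, Section 4.3 addresses them, and Section 11.0 points to the protocol as a whole. On that reading the condition in Section 4.3 qualifies the shorter sentence. This is possible but nowhere stated, and it does not close the gap: Section 4.3 then leaves the patient with no label.

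The limits on the exposed group stand. Further enhancement that prompts a change is already progression, and qualifying tissue has its own route before week 24. Section 3.0 also says: "For patients in whom pseudo-progression is suspected, continued therapy with close monitoring is recommended".

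A reader might infer that the protocol itself describes patients whose therapy is changed without tissue and whose lesions then stabilise. It does not. Section 3.0 says "For patients who are symptomatic from a growing lesion in an eloquent portion of the brain, observation is not feasible", but goes on to call for prompt diagnosis, not for an untested change of therapy. The sentence on clinical decline governs labelling, not treatment. Section 6.0 foresees resection, and that tissue may be inadequate, but allows the patient to be replaced without saying how that patient is labelled. The exposed course is an inference from these places together.

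A reader might also infer that the early-progression rule contradicts the further-enhancement rule. An interim rule followed by a final one is a plausible reading. Follow-up runs at least 11 months after PET, or 11/12 × 52.18 = 47.8 weeks, and PET follows radiation. A patient who completes it is therefore seen at least 47.8 − 24 = 23.8 weeks beyond week 24.

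**Conclusion.** The inconsistency is real and lies in the reference standard for the second primary objective. Its consequence is conditional. If one of six patients follows the exposed course, the expected SUV difference falls by 33% (true 2 vs 4) or 25% (true 3 vs 3), toward no difference. This assumes that the hypothesis about uptake is right and that the patient is typical of recurrences. If such a patient had lower uptake than other recurrences the loss would be smaller; if higher, larger.

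The documents give no frequency for this course, so they support no probability that it occurs among the six and no estimate of bias in a later study. It would be too strong to say that the planned comparison is biased; it is exposed to bias. No test, power calculation or decision threshold for the study depends on the label, and the study is declared non-definitive. Severity is minor to moderate.

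**What to change.** - Reconcile Sections 4.3 and 7.2 into one outcome definition and cite it by number in Section 11.0.
- Carry the therapy condition already in Section 4.3 into the last sentence of the Section 7.2 definition.
- Report as indeterminate any lesion that stabilises or shrinks after a therapy change or resection without qualifying histology. This also fills the gap that Section 4.3 leaves.
- Show the SUV comparison with and without indeterminate lesions. The version with them should keep the Section 7.2 label.

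The cost is protocol wording, with no added scans, visits or staff. One version of the comparison may rest on five or fewer patients. It may also set aside some true pseudoprogression cases whose therapy happened to change and which Section 7.2 would have labelled correctly. For one patient set aside, the standard error rises by the 12% or 5% shown above; hence both versions should be reported.

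Two further clarifications are optional and not part of this defect: whether the week-24 sentence is an interim rule, and whether histology overrides the imaging label in both directions.

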Choline Metabolism: Choline is a quaternary (hydrophilic) amine and is an “essential” nutrient that must be obtained from the diet. Choline is predominantly utilized for the synthesis of essential lipid components of cell membranes (e.g., phosphatidylcholine (PtdylC) and sphingomyelin), the production of potent lipid mediators (such as platelet-activating factor and lysophosphatidylcholine), and for the synthesis of the cholinergic neurotransmitter acetylcholine (ACh). PtdylC is the most important metabolite of choline and accounts for approximately one-half of total membrane lipid content and is the largest fraction of choline metabolites.[16]

Choline is initially transported into the cell and then phosphorylated by choline kinase, forming phosphocholine (PCho). Choline transporters and choline kinase are frequently overexpressed in malignancy.[17-23] PCho is readily detected by ³¹P magnetic resonance spectroscopy (MRS),

and elevated levels of “choline” ($\text{C}-\text{NH}_3)_3$ moieties are detected by ^1H MRS. These measures have been used as surrogate markers for tumors, but elevated levels are also found in many rapidly dividing cells. MRS imaging of elevated choline has been shown in numerous studies of breast, brain, and prostate tumors and is a marker of malignancy.[24-29]

Fluorocholine imaging: ^{18}F -FCH has demonstrated utility for imaging a variety of neoplasms, including those of the breast, prostate, liver and brain. Imaging metastatic and primary brain tumors with ^{18}F -FCH has also been demonstrated (**Figs. 1-3, Table 1**). The results summarized in **Table 1** demonstrate that ^{18}F -FCH uptake in primary brain tumors is very high, and most important, that uptake is very low in “benign” brain inflammatory lesions (e.g. demyelinating disease and radiation necrosis), as well as in normal brain tissue.[30]

Table 1. ^{18}F -FCholine PET data [30]

Parameter	High-grade Gliomas (n=13)	Benign Lesions (n=9)	P Value
SUV _{max} *	1.89 \pm 0.78	0.59 \pm 0.31	<.0001
White matter SUV	0.40 \pm 0.13	0.46 \pm 0.20	.58
Lesion/Brain Ratio*	5.15 \pm 2.51	1.28 \pm 0.32	<.0001

* pairwise comparisons were significant.

[figure not shown]

Figure 1. Glioblastoma: Contrast enhanced MRI (left) and ^{18}F -FCholine PET (right). Note visualization of an infiltrating portion of the tumor on the FCH PET image (arrow), that is not seen on the contrast enhanced MRI. Also note the low background activity in non-tumor normal brain regions [20].

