Comparison to ^{11}C -Choline: The imaging characteristics (e.g., tumor/brain) of ^{18}F -FCH and ^{11}C -Choline are similar (**Fig. 2**). Although there are advantages to ^{18}F -FCH, including the longer physical half-time of ^{18}F ($t_{1/2}=110$ min) compared to ^{11}C ($t_{1/2}=20$ min) and the slightly greater *in vivo* stability of ^{18}F -FCH[31, 32], radiation exposure (dosimetry) is significantly less with ^{11}C -Choline (approximately 1/5 that of ^{18}F -FCH), allowing repetitive ^{11}C -Choline studies. In addition, ^{11}C -CH is produced frequently (several times each week) for prostate cancer imaging studies at MSKCC. Furthermore, an IND for ^{11}C -CH PET imaging has been approved for these studies.

[figure not shown]

Figure 2. ^{18}F - and ^{11}C -Choline PET scans were similar at 5 and 20 minutes post-injection in a glioblastoma. However, the Tumor/Brain ratio (T/B) of ^{18}F -Choline increased with time, whereas the ratio of ^{11}C -Choline was constant. As a consequence, the T/B ratio of ^{18}F -Choline at 20 minutes post-injection was higher, ranging from 13.2 to 21.1 (16.2 +/- 2.6, seven cases) in glioblastoma [31].

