5.1 Subject Inclusion Criteria

- Age \geq 18 years
- Patient is able to provide written informed consent prior to study registration
- Histologically-confirmed high-grade glioma
- Completion of treatment with standard radiation (with or without concurrent therapy).

- Standard gadolinium-enhanced MRI changes that are considered indeterminate for tumor progression vs. treatment-related changes by the neuroradiologist or clinician within 24 weeks of completion of radiation.

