6.0 RECRUITMENT PLAN

Patients for this study will be recruited by physicians from the Departments of Neurology. Approximately 300 patients with high grade gliomas treated with radiation with or without concurrent therapy are seen a year. Approximately 30-40% will develop progressive radiographic changes on MRI brain concerning for tumor progression, typically within the first 24 weeks following completion of treatment with radiation. Of those patients approximately 30-40% will have pseudoprogression as opposed to true tumor progression. A small percentage of these patients will require surgical intervention for symptom management. We expect to enroll 6 patients over a one year period who require surgical resection of the lesion for management of progressive symptoms or if there is clinical need to establish a histologic diagnosis. Additional patients may be enrolled to replace a previously enrolled patient should surgical resection not yield adequate tissue to complete the histopathologic metrics required for the second objective of the study.

All adult patients ≥18 years are eligible for participation regardless of sex or race. Every effort will be made to encourage eligible women and minorities to enroll in this study. Prior to study entry, the study staff will explain to each potential subject the research objectives, risks and benefits of study participation, alternative treatments available, and the subjects' rights and responsibilities. If the patient agrees to participate in the study, informed consent will be obtained by a consenting individual on the study. All patients must sign written informed consent prior to being registered on this protocol.

The principal investigator may also screen the medical records of patients with whom they do not have a treatment relationship for the limited purpose of identifying patients who would be eligible to enroll in the study and to record appropriate contact information in order to approach these patients regarding the possibility of enrolling in the study.

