7.0 ASSESSMENT/EVALUATION PLAN

7.1 PRE-IMAGING EVALUATION

The following tests and procedures need to be performed within 14 days of study registration unless stated otherwise:

- History and Physical exam, including Neurologic exam
- MRI brain with/without contrast with findings consistent with radiographic progression versus pseudoprogression.
- Laboratory studies obtained as part of standard clinical care
 - Serum creatinine
 - Serum pregnancy test (women of childbearing potential) within 7 days of the first PET scan

7.2 ¹¹C-CH PET imaging and injection

All patients will undergo a single head PET/CT scan, measuring ¹¹C-CHradioactivity. This PET scan will be performed within 2 weeks of the brain MRI that demonstrates radiographic findings concerning for true tumor progression vs pseudoprogression. Various metrics derived from this data (including simple threshold SUV values) will be assessed for their ability to differentiate between pseudoprogression and recurrent tumor as confirmed by the evolution of the lesion on subsequent standard of care surveillance MRIs.

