PET Imaging Analysis. The procedures described above will yield a number of parameters that individually or in specific combinations will be assessed in their ability to distinguish treatment related changes from recurrent tumor. A positive ¹¹C-CH PET study, one which is believed to indicate recurrent tumor, is one in which there are visible focal "hot spots" (a focus of lesion/normal white matter ratio >1.4) of ¹¹C-CH.

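### Is the PET positivity cut-off of 1.4 set too low, given that it lies within the spread of benign lesions in the protocol's own Table 1?

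*Combined protocol and SAP*

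**What the plan says.** Section 7.2, under *PET Imaging Analysis*, treats a scan as positive, and as pointing to recurrent tumor, when there are visible focal hot spots, glossed in parentheses as "a focus of lesion/normal white matter ratio >1.4". The text available for review gives no source and no expected error rate for 1.4, and it contains no other numeric PET cut-off.

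The same paragraph says that the imaging parameters "individually or in specific combinations will be assessed in their ability to distinguish treatment related changes from recurrent tumor". The opening of Section 7.2 says much the same: "Various metrics derived from this data (including simple threshold SUV values) will be assessed for their ability to differentiate" between the two diagnoses.

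Section 9.0 (Primary Outcomes) compares peak lesion SUV and the tumor-to-background ratio with the MRI-based outcome. Section 11.0 (Biostatistics) summarises mean SUV, SUVmax and the lesion-to-normal ratio. Neither mentions 1.4. Sections 1.0 and 11.0 describe the data as preliminary, and Sections 1.0, 3.0 and 7.2 rule out use of the scan in patient management.

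**The concern.** Section 3.0 uses Table 1 to argue that choline uptake is very low in benign inflammatory lesions. Yet Table 1 puts the benign lesion/brain ratio at 1.28 ± 0.32, so a cut-off of 1.4 sits inside the benign distribution. On its face, the protocol's evidence predicts that a sizeable minority of benign lesions would be labelled tumor.

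The sample makes this look worse. Section 6.0 expects that "Of those patients approximately 30-40% will have pseudoprogression as opposed to true tumor progression", which is 1.8 to 2.4 of six patients, or about two. With so few benign cases, one false-positive call could colour how the pilot is read, and it could be blamed on the tracer when the cut-off alone would have predicted it.

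**Working it through.** The plan states no sensitivity, specificity or false-positive rate for 1.4, so there is no design figure to reproduce. The check asks what Table 1 implies.

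**Inputs.** Cut-off 1.4 (Section 7.2). From Table 1 in Section 3.0: benign ratio 1.28 ± 0.32, n=9; high-grade glioma ratio 5.15 ± 2.51, n=13; benign SUVmax 0.59 and white matter SUV 0.46; glioma SUVmax 1.89 and white matter SUV 0.40.

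**Is ± an SD?** The table does not say. Read as SD, a two-sample t-test on the ratio row gives p = 0.0001-0.0002, close to the tabulated <.0001. Read as SE, it gives p = 0.15-0.22. SD is the likelier reading. The table's footnote on pairwise comparisons hints at an overall test across more groups, so this check is supportive rather than conclusive.

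**Is the denominator the same?** Table 1 says lesion/brain; Section 7.2 says normal white matter. For benign lesions 0.59/0.46 = 1.28, which matches the table. For gliomas 1.89/0.40 = 4.73 against 5.15, a factor of 0.917. The match is approximate.

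**Benign lesions above 1.4.**
- Distance: (1.4 − 1.28)/0.32 = 0.375 SD.
- Normal: 1 − Φ(0.375) = 35.4%.
- Log-normal, moment-matched: log SD = √ln(1 + (0.32/1.28)²) = 0.246; log mean = ln 1.28 − 0.246²/2 = 0.217; (ln 1.4 − 0.217)/0.246 = 0.487, giving 31.3%.
- Gamma: 32.8%. Predictive t (8 df, allowing for n=9): 36.6%.
- 95% interval from the noncentral t (8 df, statistic 0.375 × √9 = 1.125): 14.9-62.3% normal. The same method on the log scale gives 12.1-58.7%.

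**Carry-over.** These intervals cover only sampling error in nine lesions.
- Scaling the benign mean and SD by 0.917 either way gives about 20-50%.
- Shifting them by 20% either way gives 7-64%.

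**In six patients.** With two pseudoprogression cases, the expected number of false positives is 2 × 0.313 to 2 × 0.354, or 0.63-0.71. At 35.4%, the chance of at least one is 1 − 0.646² = 58%. Over the 7-64% range, the chance of none runs from about 0.93² = 86% to 0.36² = 13%.

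**What 1.4 buys, and what a stricter cut-off would cost.** Take benign mean + 2 SD = 1.28 + 0.64 = 1.92 as the comparison.

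| | above 1.4 | above 1.92 |
|---|---|---|
| Benign (four models) | 31-37% | 2-7% |
| Glioma, Table 1 (normal / log-normal) | 93.2% / 99.5% | 90.1% / 97.2% |
| Glioma, mean and SD halved (normal / log-normal) | 82.5% / 86.2% | 69.9% / 65.7% |

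The stricter cut-off loses 2-3 points of sensitivity on Table 1 values, and about 13-20 points if 11C-choline tumor ratios were half as large. The halving is an assumption used to show the range.

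**The case for a change.** The strongest case for a change is that 1.4 is the only threshold with both a number and a meaning attached. The protocol itself invites the comparison by offering Table 1 as rationale and by describing the two tracers' imaging characteristics as similar. On that view, labelling the call exploratory, fixing a second cut-off such as 1.92 before any scan is read, and stating that false positives at 1.4 will not count against the tracer would cost only a few sentences.

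The overlap with the benign spread stands. The rest is weaker:

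- **Transfer is uncertain.** The benign examples named beside Table 1 are "demyelinating disease and radiation necrosis", not pseudoprogression. The Figure 2 caption says the 18F tumor/brain ratio "increased with time, whereas the ratio of" 11C-choline stayed constant. It also gives 18F ratios at 20 minutes "ranging from 13.2 to 21.1 (16.2 +/- 2.6, seven cases) in glioblastoma", where 16.2/5.15 = 3.1 times the Table 1 mean. Ratios clearly depend on method.
- **A cut-off of 1.92 has the same foundation.** It comes from the same nine lesions. If Table 1 transfers poorly, neither the criticism of 1.4 nor the alternative holds. If it transfers well, choosing between them is a preference between sensitivity and specificity.
- **Case mix is unknown.** Enrolment is of lesions "considered indeterminate for tumor progression vs. treatment-related changes", so the 30-40% from Section 6.0 may not apply.
- **A one-sided reading rule would do harm.** Discounting false positives in advance, with no matching rule for false negatives, would shield the study's hypothesis from contrary evidence.
- **One ambiguity is minor.** If *visible* is a condition separate from the ratio, one in three is an upper figure. This is a detail that readers of six scans can settle and report.

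**Conclusion.** The figures are right but no change to the plan is needed. The 31-35% benign exceedance follows from Table 1 if ± is SD, if lesion/brain and lesion/white matter ratios are interchangeable, and if nine 18F-fluorocholine lesions represent 11C-choline uptake in pseudoprogression. The last assumption is weak enough to widen the range to at least 7-64%.

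Even at face value, the effect stops at a binary label on which no stated analysis depends. The planned measures are continuous and are already set against MRI outcome. Thresholds are already to be explored, and with six ratios in hand any reader can apply any cut-off. Calling 1.4 exploratory in a study already declared non-definitive would alter no result. A low cut-off that catches about 93-99.5% of gliomas on Table 1 values is a fair trade-off for a first look.

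Part of Section 3.0 was not available for review, so a justification for 1.4 may exist there. The conclusion does not depend on it.
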